**PAGE 64 OF 287** 

# Lung Function Parameters

Actual values as well as the change from the Baseline Visit in observed and % predicted FVC, observed and % predicted  $FEV_1$ , absolute and % predicted  $FEV_1$ /FVC ratio and observed and % predicted DLCO will be presented for each visit.

The DLCO value is reported in either traditional units (mL/min/mmHg) or SI units (mmol/min/kPa). Values in SI units can be multiplied by 2.987 to obtain values in traditional units [37].

## Mobility change

Any movement mobility change (better/the same/slightly worse/moderately worse/severely worse movement) will be summarised by body locations and annually.

Actual values as well as the change from the Baseline Visit in number of impacted locations per patient will be presented annually.

The evolution of impacted location will be presented annually by summarising for each location (some grouping might be done) the number of times the location is impacted.

Movement mobility outcomes (change in extra bone growth, change in movement), causes, associated symptoms if preceded by a flare-up will be summarised by location.

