# 9.3.1.2 Secondary Endpoints

For participants with FOP exposed and unexposed to palovarotene:

- Raw values and change from Baseline in CAJIS total score at each Follow-up Visit;
- Raw values and shift from Baseline in use of assistive devices and adaptations for daily living at each Follow-up Visit;
- Raw values and change from Baseline in % of worst score for total score, upper extremities subscore and mobility subscore using age-appropriate forms of the FOP-PFQ at each Follow-up Visit;
- Raw values and change from Baseline in observed and % predicted FVC at each Follow-up Visit;
- Raw values and change from Baseline in observed and % predicted FEV1 at each Follow-up Visit;
- Raw values and change from Baseline in absolute and % predicted FEV1/FVC ratio at each Follow-up Visit;

PAGE 51 OF 287

- Raw values and change from Baseline in observed and % predicted DLCO at each Follow-up Visit;
- Raw values and change from Baseline in physical and mental function (mean global physical and mental health score converted into T-scores) for participants ≥15 years old and overall QoL (mean total score converted into T-scores) for participants <15 years old using age-appropriate forms of PROMIS Global Health Scale at each Follow-up Visit;
- Annualised frequency of flare-ups, categorised by overall occurrence;
- Number of locations impacted by movement mobility change per participant annually and change from Baseline;
- Any movement mobility change (better movement/the same movement/slightly worse movement/moderately worse movement/severely worse movement) by body location and annually;
- Evolution of locations impacted by movement mobility change (how many times a location is impacted) per body location, annually and change from baseline;
- Movement mobility outcomes (change in extra bone growth and change in movement), causes, associated symptoms if preceded by a flare-up event by body location;
- Frequency, severity, outcome and descriptive characteristics of any fractures, overall and at each Follow-up Visit, categorised by location;
- Annualised frequency and descriptive characteristics of bone fractures, categorised by overall occurrence and location;
- Incidence of pregnancy.

For participants with FOP exposed to palovarotene who become pregnant while enrolled in FOPal:

- Pregnancy characteristics and outcomes;
- Pregnancy-related AEs through the first year postpartum;

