#### Movement Mobility Change

For each movement mobility change, the impacted location, start date, causes, the outcome (change in extra bone growth, change in movement and associated flare-up event, if any) at the Baseline Visit and Follow-up/End of Study associated Visits if available. Movement mobility history over the past 12 months prior to the Baseline Visit will also be collected at the Baseline Visit.

Symptoms associated with flare-ups include, but are not limited to, pain, swelling, stiffness, redness, warmth, fever, lethargy, loss of appetite, decreased range of motion and change in mood or behaviour.

At each visit, the investigator will ask the participant if they experienced any movement mobility change since their last visit.

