#### 9.7.3.1 Statistical Analyses – General Considerations

The statistical analyses will be performed by an external SP, managed by the sponsor's Medical Affairs Biometry Department.

Statistical evaluation will be performed using Statistical Analysis System (SAS)® (Version 9.2 or higher).

No formal statistical testing will be performed and all the analyses will be primarily descriptive in nature. When appropriate and unless otherwise specified, 2-sided 95% CI will be displayed and if p-values are presented, they will be for exploratory purposes only.

Descriptive summary statistics will include the number of documented data, number of missing data and the following:

- Mean, standard deviation, 95% CI of the mean/median when appropriate, median, minimum and maximum for continuous variables;
- Frequency count and percentages for categorical nominal variables.

Missing data will not be replaced but will be summarised in all relevant tables.

Percentages will be based on the number of non-missing observations.

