# 9.7.3.3 Analysis of Secondary Endpoints – Effectiveness Evaluation

Effectiveness data will be included in the participant data listings using the Safety Exposed and the Safety Unexposed Populations. Analyses and summary tables will be presented in the Safety Exposed and the Safety Unexposed Populations.

Data will be tabulated descriptively, i.e. the number and percentage of participants for each category for categorical parameters and the number, mean, standard deviation, 95% CIs of the mean/median when appropriate, median, minimum and maximum for continuous parameters will be tabulated.

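### The yearly count of how often each body location is impacted has no denominator for participants or time observed, so it tracks cohort size rather than risk

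*Protocol*

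**What the plan says.** The Mobility change part of protocol section 9.7.3.3 describes four outputs:

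- The five-level movement category, from better to severely worse, "will be summarised by body locations and annually".
- The number of impacted locations: "Actual values as well as the change from the Baseline Visit in number of impacted locations per patient will be presented annually".
- Evolution by location: this output "will be presented annually by summarising for each location (some grouping might be done) the number of times the location is impacted".
- Outcomes, causes and symptoms: "associated symptoms if preceded by a flare-up will be summarised by location". This one is not annual.

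The endpoint behind the third output is listed in 9.3.1.2 as "Evolution of locations impacted by movement mobility change (how many times a location is impacted) per body location, annually and change from baseline". The comparison with Baseline is stated there; the 9.7.3.3 sentence does not repeat it.

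Two general rules bear on denominators. The opening of 9.7.3.3 calls for "the number and percentage of participants for each category for categorical parameters". Section 9.7.3.1 says: "Percentages will be based on the number of non-missing observations".

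On data capture, 9.3.2.8 describes details recorded for each mobility change. It adds that at every visit the participant is asked "if they experienced any movement mobility change since their last visit".

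**The concern.** The third output takes the body location as its unit and counts events across the cohort. Nothing in either definition brings in how many participants were observed that year, or for how long. Its neighbours in 9.3.1.2 are handled differently: flare-ups and bone fractures are annualised frequencies, and impacted locations are per participant.

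The number observed will vary a great deal. Section 9.2.4 allows up to 10 years of enrolment in a study of up to 11 years, with at least 1 year of data per participant. Under 9.2.8, exposed participants generally leave when they are no longer receiving palovarotene (a safety concern or pregnancy is excepted). Unexposed participants leave on pregnancy or on starting another FOP treatment. A yearly total, and its change from Baseline, can therefore move substantially with no change in risk, and by different amounts in the two cohorts. Mobility is reported as effectiveness, so a falling total could be read as benefit.

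A smaller, related gap concerns the five-category output. Details are recorded per change, and percentages use non-missing observations. A participant with no change at a location may have no record there and drop out of the base.

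**Working it through.** The protocol gives no mobility event rate and no retention figure, so there is no stated number to reproduce. The calculation below is an illustration.

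**Inputs from the protocol.** N = 67 exposed and 33 unexposed (minimum, 9.5); enrolment 10 years, study 11 years (9.2.4).

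**Assumptions, not in the protocol.** Uniform enrolment; a constant true rate of 0.3 impacts per participant-year at one location; yearly exit of 0%, 10% or 20%.

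**Formula, by follow-up year k.** Expected count = 0.3 × N × ∫ S(t)·exp(−ht) dt over t from k−1 to k. Here S(t) = 1 for t ≤ 1, S(t) = (11 − t)/10 for 1 < t ≤ 11, and h = −ln(1 − yearly exit). With no exit and k ≥ 2, the integral is (11.5 − k)/10.

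**N = 67, no exit.**

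- Year 1: 67 × 1 = 67.0 person-years; × 0.3 = 20.1.
- Year 5: 67 × 0.65 = 43.55 person-years; × 0.3 = 13.1.
- Year 10: 67 × 0.15 = 10.05 person-years; × 0.3 = 3.0.
- Fall from year 1 to year 10: 1 − 0.15 = 85%. The assumed 0.3 cancels, so this percentage does not depend on it.

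**All scenarios, expected count at one location.**

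| N | Yearly exit | Year 1 | Year 5 | Year 10 | Fall, year 1 to 10 |
|---|---|---|---|---|---|
| 67 | 0% | 20.1 | 13.1 | 3.0 | 85% |
| 67 | 10% | 19.1 | 8.1 | 1.1 | 94% |
| 67 | 20% | 18.0 | 4.8 | 0.4 | 98% |
| 33 | 0% | 9.9 | 6.4 | 1.5 | 85% |

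**With person-years as denominator (N = 67, no exit).** 20.1/67.0, 13.065/43.55 and 3.015/10.05 all equal 0.30.

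**By calendar year.** With no exit, expected person-years in calendar year c (1 to 10) are 67 × (c − 0.5)/10. Year 1 gives 3.35 × 0.3 = 1.0; year 5 gives 30.15 × 0.3 = 9.0; year 10 gives 63.65 × 0.3 = 19.1. The same constant risk now produces a rising count.

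**Per-participant comparison.** Under the same assumptions, 13.4 participants enter follow-up year 10 (67 × 0.2). Impacts per participant entering the year go from 0.300 in year 1 to 3.015/13.4 = 0.225. That modest drop arises only because some of those years are partly observed.

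**Category base, invented figures.** Suppose 67 participants are asked, 20 have a recorded change at a location (one each) and 10 of those are severely worse. On recorded changes the percentage is 10/20 = 50%; on participants asked it is 10/67 = 14.9%. The two answer different questions, so the base has to be named.

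**The case against.** The strongest reply has five parts.

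- **Other mobility outputs do have a base.** A reader might infer that all the annual mobility outputs are raw totals or shares of recorded changes. The text does not support that. The number of impacted locations is per patient, and the opening of 9.7.3.3 prescribes number and percentage of participants for categorical data. This stands and limits the point to one output, plus an unclear base for another.
- **Shares do not fall because the cohort shrinks.** A reader might also infer that category percentages drift down with attrition. If they are taken over recorded changes, numerator and denominator shrink together. The possible fault is that they cannot show frequency.
- **The sentence could mean a per-participant count, summarised with n and mean.** That reading is possible. But both definitions put the count at the level of the location, and the participant wording used for the neighbouring endpoint is absent.
- **The direction is not fixed, and the recording rule is partly inferred.** The protocol does not define the year, so the count may fall or rise. The scale includes an unchanged category, and the protocol does not say how a negative answer is stored. Both stand. The first changes the sign of the artefact, not its cause.
- **This is detail for the SAP.** Section 9.7.3 is a summary, and a separate SAP is promised. Table denominators alone would be an SAP matter. Here the protocol itself fixes the metric, a count with change from Baseline, and an SAP that follows it reproduces the problem.

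Impact is also limited. The analyses are descriptive, and mobility is not among the outcomes that 9.7.3.4 selects for the weighted exposed-versus-unexposed comparison.

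**Conclusion.** The point holds for the evolution-of-impacted-locations endpoint in 9.3.1.2 and 9.7.3.3. As defined, it is driven by how many participants are observed and for how long. In the illustration, staggered entry alone lowers the expected count by 85% between follow-up years 1 and 10 at constant risk. By calendar year the count rises while enrolment builds. The 85% rests on uniform enrolment over the full 10 years and no dropout. The absolute counts also rest on the assumed 0.3 per participant-year, and the 94% and 98% figures on assumed exit rates.

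For the five-category output, the finding is only that its base is unclear between the participant rule in 9.7.3.3 and the non-missing rule in 9.7.3.1. The number of impacted locations per patient is not affected by the raw-total problem. The endpoint is secondary and descriptive, so this should be corrected but does not threaten the primary safety objective.

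**What to change.** In 9.3.1.2 and 9.7.3.3:

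- Define the evolution output as impacts per participant-year observed, for each location (or location group) and year, with the number of participants and the person-years beside each figure.
- Base change from Baseline on that rate.
- State whether years are follow-up or calendar years.
- For the five-category output, state that the percentage base is participants assessed in that year, and show those reporting no change as an explicit row.

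The cost is wording, table shells and minor programming. Person-time can be built from visit dates. One thing needs confirming: 9.3.2.8 says the question is asked at each visit, but not that a negative answer is stored in the eCRF. If it is not, a field for it is needed so that participants assessed can be counted.

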# 9.7.3.4 Analysis of Secondary Endpoints – Key Safety Outcomes Evaluation

All key safety outcomes will be included in the participant data listings using the appropriate Safety Populations. Analyses and summary tables will be presented using the appropriate Safety Populations.

# Flare-ups

The number of flare-ups over the past 12 months prior to baseline and since the last visit will be presented for each visit.

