**PAGE 36 OF 287** 

As this is a non-interventional, observational registry study designed to collect and assess real-world data, exposed participants will receive palovarotene as prescribed by their treating physician, as per local label. Palovarotene will be supplied to the participant according to usual practice, not by the sponsor.

In addition, participants will be treated in accordance with usual medical practice during their participation in the FOPal registry study. No additional assessments or tests will be required by this protocol. All relevant data collected as part of routine medical care will be captured using the electronic Case Report Form (eCRF) by the investigator (patient-reported questionnaires will be completed directly by the participant on paper and returned to the site for data entry into the eCRF) and transmitted to the sponsor. If some assessments are not routinely performed by the investigator, they will not complete the corresponding sections in the eCRF.

The FOPal registry study will collect data at Baseline and at each Follow-up Visit. Follow-up Visits are scheduled as per routine clinical practice (recommended every 6 months).

The duration of the FOPal registry study is up to 11 years, with an enrolment period of maximum 10 years from first participant, first visit, and a minimum of 1 year of data collected for participants who are enrolled within that period.

The primary objective of the FOPal registry study is to collect and assess real-world safety data in participants with FOP exposed to palovarotene, to permit the description and incidence of all treatment-emergent adverse events (TEAEs), serious TEAEs and nonserious TEAEs, whether or not they are considered related to palovarotene and all serious and nonserious treatment-related TEAEs.

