**PAGE 40 OF 287** 

- a Follow-up Visits are recommended every 6 months, or as per local label.
- b If participant <18 years (or the legal age of consent in the jurisdiction in which the study is taking place), assent and parent or legally authorised representative consent will also be required.
- c This includes a general assessment, dermatologic, lymph nodes, HEENT, chest, cardiac, abdomen, limb/extremities, musculoskeletal, neurologic and other.
- d Not expected in the context of a telephone/video visit.
- e Collected for growing children. Assessment as per local label.
- f Linear height within 6 to 12 months prior to and at the Baseline Visit.
- g Vital signs to be collected are respiratory rate, blood pressure and heart rate.
- h Participants will be assessed for child-bearing status and pregnancy prevention measures. As per local label, pregnancy testing is carried out with a confirmation of absence of pregnancy monthly if the participant receives palovarotene and one month after stopping. These conditions also concern participants who are not currently sexually active unless the prescriber considers that there are compelling reasons to indicate that there is no risk of pregnancy.
- i This includes a period of two months prior to the signed informed consent date.
- i Not applicable for pregnant participants.
- k Spirometry obtains the lung function parameters of observed and % predicted FVC and FEV1 and the absolute and % predicted FEV1/FVC ratio. The DLCO test obtains observed and % predicted DLCO which provides information on the efficiency of gas transfer from alveolar air into the bloodstream.
- 1 This includes number of flare-ups over the past 12 months before the signed informed consent date.
- m Spinal health assessment to be performed using radiological imaging (e.g. CT, X-ray, scintigraphy, etc).
- n AE, SAE, Special Situation and AESI collection begins once the informed consent has been signed.
- o Paper-based patient-reported questionnaires.

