#### Flare-ups

At Baseline, the investigator will ask the participant how many flare-ups they experienced over the past 12 months. At each Follow-up Visit, the investigator will ask the participant how many flare-ups they experienced since the last visit.

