#### 9.4 Data Sources

Source data includes any data collected as part of routine medical care which will be captured in an eCRF by the investigator and transmitted to the sponsor for analysis. The patient-reported questionnaires (FOP-PFQ, PROMIS Global Health Scale and FOP assistive devices assessment) will be completed directly by the participant or proxy on paper (see Section 9.3.2.8).

In observational studies like FOPal, data collection relies on several stakeholders: 1) investigators and site staff; 2) Healthcare professionals (HCPs) including general practitioners (GP), paediatrician, other physicians and home nurses; and 3) patients. Sponsor consultation with physicians who are expert in managing FOP confirms that in the real-world setting, while formal in-person visits may be scheduled annually, patients are also in contact with these experts throughout the year on an ad hoc basis for many aspects of FOP care. Active data collection is only managed via the sites and the sponsor has multiple strategies to ensure the sites regularly provide structured data collection. This active data collection process is summarised in Figure 3.

[figure not shown]

Figure 3 Active data collection process flow

Abbreviations: GP= General practitioner, HCP= Healthcare professional, PI= Principal Investigator.

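### The only descriptive flare-up summary in Section 9.7.3.4 shows raw counts over unequal time windows, although the endpoint is an annualised frequency

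*Protocol*

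**What the plan says.** The secondary endpoint for both cohorts in Section 9.3.1.2 is "Annualised frequency of flare-ups, categorised by overall occurrence". The comparison of key safety outcomes in Section 9.7.3.4 names the same annualised measure.

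The Flare-ups paragraph of Section 9.7.3.4 plans something else: "The number of flare-ups over the past 12 months prior to baseline and since the last visit will be presented for each visit". The statistic is a number of events, displayed visit by visit. No rate, denominator or interval length is mentioned.

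Section 9.3.2.8 (Flare-ups) confirms the two recall windows: "At Baseline, the investigator will ask the participant how many flare-ups they experienced over the past 12 months", and then "At each Follow-up Visit, the investigator will ask the participant how many flare-ups they experienced since the last visit".

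The length of the second window is not fixed. Table 2, note a, says "Follow-up Visits are recommended every 6 months, or as per local label". Table 3 carries the same note, and Table 4 recommends 6 months for unexposed participants. Section 9.2.6 makes clear that assessments are not mandated. Section 9.4 reports that, in practice, "while formal in-person visits may be scheduled annually, patients are also in contact with these experts throughout the year on an ad hoc basis".

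The baseline window for exposed non-naïve participants is described in more than one way. Section 9.3.2.1 starts it 12 months before the first marketed dose and runs it on to the consent date. Table 3, note l, gives the 12 months before the first marketed dose. Section 9.3.2.8 and the Flare-ups paragraph of Section 9.7.3.4 speak simply of 12 months.

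**The concern.** A count of events means little without the time over which it was gathered. In this table the first column carries 12 months of recall, and each later column carries whatever time has passed since the previous visit, which may differ between participants and between visits. Anyone reading along the row sees the change in window length mixed with any change in flare-up rate, and the plan does not say that the window length will be shown.

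The summary also fails to produce the endpoint it sits under. The authors annualise or set yearly periods elsewhere: height velocity in Section 9.7.3.4 is annualised with a rule on spacing between measurements, and mobility change in Section 9.7.3.3 is summarised annually. Flare-ups receive neither treatment in their descriptive paragraph.

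Flare-ups are one of three named key safety outcomes. If follow-up is mostly 6-monthly, the summary would display a fall after baseline in both cohorts even if nothing had changed.

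**Working it through.** The protocol gives no flare-up rate and no figure to reproduce. The check is therefore what the planned table would show if the underlying rate were constant and nothing affected it.

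**Inputs**
- Baseline window: 12 months (Sections 9.3.2.8 and 9.7.3.4).
- Follow-up window: time since last visit. The recommended interval is 6 months (Section 9.1; Tables 2 to 4, note a); annual in-person visits are described in Section 9.4.
- Other intervals (3 and 9 months), the mix of intervals, and the 18- and 24-month non-naïve windows are assumptions.
- Flare-up rate: not given. Values of 1, 2 and 3 per year are assumed; the ratio does not depend on the choice.

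**Formula.** Expected count = rate × window. With the same rate throughout, the rate cancels:

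expected follow-up count / expected baseline count = follow-up window / baseline window.

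**12-month baseline window**

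| Follow-up interval | Ratio | Apparent change |
|---|---|---|
| 3 months | 3/12 = 0.25 | −75% |
| 6 months | 6/12 = 0.50 | −50% |
| 9 months | 9/12 = 0.75 | −25% |
| 12 months | 12/12 = 1.00 | 0% |

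At an assumed 2 flare-ups per year, the table would show 2 × 1.0 = 2.0 at baseline and 2 × 0.5 = 1.0 at a 6-month visit.

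**Mixed intervals (assumed).** With 10% of intervals at 3 months, 50% at 6, 20% at 9 and 20% at 12: 0.10 × 0.25 + 0.50 × 0.50 + 0.20 × 0.75 + 0.20 × 1.00 = 0.625.

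**Longer non-naïve baseline (assumed).** If the window runs to consent and comes to 18 or 24 months, a 6-month visit gives 6/18 = 0.33 or 6/24 = 0.25.

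**Simulation.** Poisson counts with gamma-distributed individual rates gave 6-month to baseline ratios of 0.501, 0.500 and 0.499 for mean rates of 1, 2 and 3 per year, 12-month ratios of 1.002, 0.999 and 0.999, and mixed-interval ratios of 0.626, 0.624 and 0.625.

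**After dividing by time.** At a true rate of 2 per year, the simulated annualised rate was 2.004 at baseline, 2.005 with 6-month visits and 2.002 with the mixed intervals. The artefact disappears.

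**The case against.** The strongest reply is that the measure that matters is already right. The endpoint in Section 9.3.1.2 and the weighted exposed-unexposed comparison in Section 9.7.3.4 both use annualised frequency. This stands, and it confines the problem to the descriptive visit table.

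Second, no change from baseline is planned for flare-ups, unlike CAJIS, lung function or growth, and the sentence names both windows. This is also true. A reader has to draw the contrast, but a table by visit that opens with baseline invites it.

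Third, Section 9.7.3 calls itself a summary and leaves technical detail to the SAP. How intervals are computed can be left there. This sentence, however, does not leave the statistic open: it specifies a number of events, and that differs from the endpoint.

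Two stronger readings are tempting.

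- A reader might infer that the table will always show a halving. The documents do not support that: the 50% figure belongs to 6-month visits, and with the annual visits mentioned in Section 9.4 the ratio is 1.00.
- A reader might infer that more frequent visits in the exposed cohort would make palovarotene look better than no treatment. The protocol nowhere shows that exposed visits are more frequent. No label interval is given, and 6 months is recommended for unexposed participants too. With both cohorts at 6 months the per-visit counts are comparable, and the planned between-cohort comparison is annualised in any case.

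**Conclusion.** The point holds for the descriptive visit table only. The Flare-ups paragraph of Section 9.7.3.4 sets a 12-month baseline count beside follow-up counts of variable length and does not match the annualised endpoint. The size depends wholly on the visit interval: an apparent fall of 50% at the recommended 6 months, 25% at 9 months, and none with annual visits. These figures assume a constant rate, no effect, complete recall and a 12-month baseline window; they do not depend on the rate itself. For exposed non-naïve participants the fall could be larger if the baseline window runs to consent, by an amount the protocol does not allow one to calculate.

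No bias between cohorts, and none in favour of palovarotene, is established. This is a modest correction to a stated rule, and it does not undermine the planned comparison of exposed and unexposed participants.

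**What to change.** Reword the Flare-ups paragraph of Section 9.7.3.4 so that each visit presents flare-ups per person-year: the count divided by the time it covers. Put the baseline count on the same yearly scale, and show the interval length or total person-time beside each figure. Raw counts can remain in the participant listings.

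Reconcile the baseline flare-up window for exposed non-naïve participants across Section 9.3.2.1, Section 9.3.2.8, Table 3 note l and Section 9.7.3.4, so that the start and end of the window, and hence the divisor, are unambiguous.

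The cost is protocol wording and table shells. No new data are needed for the follow-up intervals, since Section 9.8.3 already requires visit dates in the source documents.
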